2. INTRODUCTION

2.1. Clinical Study Rationale

Ulcerative colitis (UC) is a chronic, idiopathic, inflammatory disease that affects the colon and is most prevalent in adults between the ages of 30 and 40 years. It is characterized by relapsing and remitting mucosal inflammation extending from the rectum to the proximal segments of the colon.

The etiology of the disease is believed to involve immune, genetic, environmental, and microbial factors. Discoordinated activity of both the innate and adaptive immune response in combination with defects of the epithelial barrier and dysbiosis lead to an inflammatory cascade resulting in bloody diarrhea, rectal urgency and tenesmus, and in its later stages an increased risk for colorectal cancer. Further UC extraintestinal symptoms include ocular lesions, skin lesions, arthritis, and primary cholangitis.

Historically, UC has been managed with anti-inflammatory drugs and general immunosuppressants. In the last 2 decades, approaches have become more targeted using biologics acting on tumor necrosis factor (TNF) alpha, and more recently anti-integrin and anti-interleukin (IL)-12/IL-23 antibodies.

However, while biologics have provided substantial improvements in patient therapy, about 30% of patients do not respond to biologics and a further 30 to 50% will stop responding during therapy.

A new approach to UC therapy involves orally bioavailable small-molecules inhibiting signal transduction pathways involved in UC pathogenesis, such as Janus Kinase (JAK) inhibitors. Filgotinib is a preferential JAK1 inhibitor approved for the treatment of rheumatoid arthritis and UC in the European Union (EU), United Kingdom (UK), and Japan.

While clinical data indicate that response to 200 mg filgotinib once daily (q.d.) is more rapid and pronounced compared to 100 mg filgotinib q.d. in subjects with moderate to severely active UC, maintenance of clinical remission may be achieved at a lower dose.

This study will explore the possibility of dosing flexibility in subjects who are in clinical remission on 200 mg filgotinib q.d. in the SELECTION-LTE (GLPG0634-CL-307) study.

For more details refer to the latest version of the investigator's brochure (IB) and its relevant updates/addenda.

This clinical study will be conducted in compliance with this clinical study protocol (CSP), the current International Council for Harmonisation of Technical Requirements for Pharmaceuticals for Human Use – Good Clinical Practice (ICH-GCP) Guideline E6, and applicable local ethical and legal requirements (see also Section 12).

2.2. **Background - Nonclinical Studies**

For nonclinical pharmacology, PK, and toxicology data of filgotinib, refer to the IB (Section 1, Company Core Data Sheet).

2.3. **Background - Clinical Studies**

The efficacy and safety of 200 mg and 100 mg filgotinib q.d. in 1351 subjects with moderately to severely active UC were evaluated in a randomized, double-blind, placebo-controlled combined Phase 2b/3 study over a duration of 58 weeks (SELECTION, GS-US-418-3898). The study combined 2 consecutive substudies: an induction study assessing subject response at Week 10 and a maintenance study continuing until Week 58. Subjects who achieved either endoscopy/bleeding/stool (EBS) remission or Mayo Clinical Score (MCS) response at Week 10 of the induction study were re-randomized into the maintenance study.

A significant number of subjects receiving 200 mg filgotinib q.d. achieved clinical remission at the end of the induction study compared to placebo. At Week 58 and the end of the maintenance study, significance was achieved by both the 200 mg q.d. and the 100 mg q.d. cohort.

A long-term extension (LTE) study (SELECTION-LTE, GS-US-418-3899, GLPG0634-CL-307) is ongoing in 1161 subjects who have completed the SELECTION study. Subjects who did not achieve EBS remission or MCS response as well as subjects who met the prespecified definition of disease worsening during the SELECTION study were given the option to receive open-label 200 mg filgotinib in the SELECTION-LTE study.

Filgotinib 100 mg and 200 mg q.d. were generally well tolerated in both studies. In an integrated safety analysis based on results of the SELECTION study and interim results of the SELECTION-LTE study, including 1253 subjects, no significant differences between treatment groups in occurrence of adverse events (Aes), serious Aes (SAEs), or Aes leading to study discontinuation could be found. Rates of serious infections, herpes zoster, opportunistic infections, venous thrombosis, pulmonary embolism, malignancies, and gastrointestinal perforation were low and comparable across treatment groups. Overall, 3 deaths were reported; none of the Aes leading to death were assessed as related to filgotinib.

3. **CLINICAL STUDY OBJECTIVES**

3.1. **Primary Objective**

- To evaluate the efficacy of filgotinib in subjects in stable clinical remission on 200 mg filgotinib q.d. for whom the dose was decreased to 100 mg q.d. compared to subjects remaining on 200 mg q.d.

3.2. **Secondary Objective(s)**

- To evaluate the effect of dose de-escalation of filgotinib on time to flare.
- To evaluate the effect of dose de-escalation of filgotinib on disease-specific biomarkers and Inflammatory Bowel Disease Questionnaire (IBDQ).

- To evaluate the safety and tolerability of filgotinib.

[REDACTED]

4. ENDPOINTS AND ESTIMANDS

4.1. Primary Endpoint/Estimand

- Proportion of subjects in corticosteroid-free² clinical remission based on modified Mayo Clinical Score (mMCS)³ at Week 48.

The primary estimand for the primary endpoint targets to estimate the effect of decreasing the filgotinib dose from 200 mg q.d. to 100 mg q.d. versus remaining on 200 mg q.d. on corticosteroid-free mMCS remission without ES-confirmed flare or discontinuation of treatment at Week 48, regardless of treatment interruptions, in subjects who are in stable clinical remission at study entry. The effect size will be estimated using the Mantel-Hanszel method and expressed as a difference in proportions.

[REDACTED]

[REDACTED]

[REDACTED]

² Free of corticosteroids for at least 12 weeks.

³ mMCS score of ≤ 2 , with endoscopic subscore of ≤ 1 , stool frequency subscore of ≤ 1 , and a rectal bleeding subscore of 0.

The primary estimand for the primary endpoint is described according to the following attributes:

Primary Endpoint	Primary Estimand
Treatment	Filgotinib 100 mg q.d. and filgotinib 200 mg q.d. as randomized.
Population	Subjects who are in stable clinical remission on filgotinib 200 mg q.d. defined through the appropriate inclusion / exclusion criteria.
Variable	Binary corticosteroid-free mMCS remission without ES-confirmed flare and without discontinuation of treatment at Week 48. Corticosteroid-free is defined as free of corticosteroids for at least 12 weeks.
Intercurrent events including strategy for addressing them	
ES-confirmed UC flare: Subjects randomized to the filgotinib 100 mg q.d. or 200 mg q.d. group will be considered as nonresponders for any visit after the re-escalation visit, for flares occurring prior to Week 48 (Composite strategy).Permanent treatment discontinuation (not flare-related): Subjects who discontinue treatment prior to Week 48 will be considered as nonresponders in both the 100 mg q.d. and the 200 mg q.d. group (Composite strategy).Any temporary treatment interruption: Data collected for subjects who temporarily interrupt treatment will be included as reported in the analysis (Treatment policy strategy).
Population-level summary	The treatment difference in the percentage of subjects meeting corticosteroid-free mMCS remission criteria between the filgotinib 100 mg q.d. group and 200 mg q.d. group at Week 48.
Estimator	The adjusted proportion difference (filgotinib 200 mg – filgotinib 100 mg) with corresponding 95% confidence interval (CI) as calculated by a stratified Mantel-Haenszel test (stratification factor: baseline ES [0 or 1]).

Refer to Section 9.3.4.1 for more information.

4.2. Secondary Endpoints

- Time to PRO2 flare¹.
- Time to ES-confirmed UC flare.
- Change from baseline in C-reactive protein (CRP) and fecal calprotectin (FCP) up to Week 48.
- Change from baseline in IBDQ at Week 48.

¹ Defined as a PRO2 (patient-reported outcome based on 2 items) score worsening of at least 2 points and an absolute PRO2 score of at least 3, with stool frequency subscore ≥ 2 , and rectal bleeding subscore ≥ 1 .

- Frequency and severity of treatment-emergent adverse events (TEAEs), treatment-emergent SAEs, and TEAEs leading to treatment discontinuation.

Refer to Section 9.3.4.2 for more information.

© 2019 Pearson Education, Inc.

[REDACTED]

1 | Page

11. **What is the primary purpose of the *Journal of Clinical Endocrinology and Metabolism*?**

[View Details](#) [Edit](#) [Delete](#)

© 2019 Pearson Education, Inc.

5. INVESTIGATIONAL PLAN

5.1. Clinical Study Design

This study is a Phase 3b, randomized, double-blind, controlled, multi-center study to evaluate the efficacy and safety of dose de-escalation of orally administered filgotinib in subjects with UC in corticosteroid-free clinical remission.

Approximately 80 subjects, who are in clinical remission on 200 mg filgotinib q.d. for at least 2 consecutive quarterly visits in the ongoing SELECTION-LTE study, are planned to be rolled over and randomized (1:1) to receive either 100 mg or 200 mg filgotinib q.d. Subjects will be stratified according to ES (0 or 1) at baseline to ensure treatment balance in each stratum.

For more information, contact the Office of the Vice President for Research and Economic Development at [contact] or [contact].

11. **What is the primary purpose of the *Journal of Clinical Endocrinology and Metabolism*?**

For more information, contact the Office of the Vice President for Research and Economic Development at [contact] or [contact].

For more information, contact the Office of the Vice President for Research and Economic Development at [contact] or [contact].

The study will consist of the following study periods:

- screening period: a maximum of 28 days with at least 2 screening visits;
- treatment period:
 - During the blinded treatment period, study visits will be on Day 1 (randomization to blinded treatment), at Week 4, Week 12, and then every 12 weeks. Subjects will receive blinded treatment until the primary analysis time point (i.e. after the last subject completed their Week 48 postbaseline visit or has completed their Week 12 post re-escalation visit, or after the last follow-up of subjects discontinuing prior to Week 48, whichever comes last, see Section 6.4.2), with the exception of subjects with ES-confirmed UC flare who will be switched to open-label 200 mg q.d. (as explained below).
 - After unblinding at the study primary analysis time point, subjects will receive unblinded treatment and the frequency of study visits will be reduced to every 24 weeks (see Section 8.1.4).
- follow-up: 4 weeks after last dose (End of Study [EoS] visit).

Sigmoidoscopy

The ES will be obtained from a sigmoidoscopy performed during screening, including collection of 2 biopsies for histology assessment.

Roll-over from SELECTION-LTE

Subjects in the SELECTION-LTE study who are in clinical remission with 200 mg filgotinib q.d. for at least 2 consecutive quarterly visits, will be provided the option to roll-over to the present study at any scheduled visit of the SELECTION-LTE study or at a separate visit.

Subjects will be requested to attend the site for at least 2 screening visits. Depending on the results of FCP (if applicable) and ES at screening, the subject will either be a screening failure (FCP >250 µg/g or ES >1) in the present study and will remain in SELECTION-LTE, or the subject will be eligible (FCP ≤250 µg/g and ES ≤1) and will need to perform the End of Treatment (EoT) assessments in SELECTION-LTE before being randomized to the present study. Subjects who fail screening in the present study may be re-screened once. Re-screening may only be conducted after approval from the sponsor's medical lead (see Section 8.1.3).

Further details on the timing of screening and Day 1 assessments are provided in Section 8.1.

Flare

When a subject experiences an increase in clinical symptoms, a stool sample will be obtained for culture for pathogenic bacteria, ova and parasite evaluation, and *Clostridium difficile* toxin assay.

An endoscopy will be performed in subjects who experience during treatment an increase in clinical symptoms defined as:

- an increase in rectal bleeding subscore by at least 1 point, AND an increase in stool frequency subscore by at least 2 points, AND a *Clostridium difficile* infection is excluded.

An ES-confirmed UC flare is defined as:

- an increase in rectal bleeding subscore by at least 1 point AND an increase in stool frequency subscore by at least 2 points AND an increase in endoscopic subscore by at least 1 point.

Subjects who experience an ES-confirmed UC flare during treatment will be “re-escalated” (see [Definition of Terms](#)) to open-label 200 mg filgotinib q.d. for at least 12 weeks, while maintaining the blind for the treatment at randomization, and should follow the Schedule of Activities after re-escalation ([Section 8.9.2](#)). An ES-confirmed UC flare should be reported as an adverse event (AE), as explained in [Section 8.4.1](#).

Re-escalation

Subjects should follow the Schedule of Activities after re-escalation ([Section 8.9.2](#)).

- In case of further worsening of symptoms after Week 2 following re-escalation and/or no improvement in pMCS is detected at Week 4, addition of corticosteroid treatment (i.e. orally- and/or rectally-administered corticosteroids) can be considered with a maximum oral dose of 30 mg q.d. prednisone equivalent.
- If the subject does not respond to re-escalation therapy within a timeframe of maximum 12 weeks, the subject will be permanently discontinued from the treatment and invited to remain in the study up to Week 48 (see [Section 5.4.1.1](#)).
- If subject improvement is sufficient in the opinion of the investigator, the subject will restart the regular Schedule of Activities ([Section 8.9.1](#)), starting from the next 12-weekly visit assessments. The subject may continue on open-label 200 mg filgotinib q.d. until the end of the study. Corticosteroid treatment should be tapered off at the discretion of the investigator.

In case symptoms are worsening again after 12 weeks of re-escalation, the disease worsening criteria must be applied, as explained in [Section 5.4.1.3](#).

Study duration

Each subject will be in the study for a minimum of approximately 56 weeks (28 days screening period + 48 weeks of treatment + 4 weeks follow-up) in countries where filgotinib will become commercially available, and for a maximum duration of 216 weeks (approximately 4 years) in case filgotinib will not become commercially available. In case of re-escalation, the subject will remain in the study at least until the next regular scheduled visit after the 12 weeks post re-escalation visit, or until the end of the study in that country, whichever is longer.

In countries where filgotinib becomes commercially available, the study will be terminated for the subjects who have already completed at least 48 weeks of treatment. Subjects will then be requested to attend the EoT visit as soon as possible. For the subjects who have not yet completed

the Week 48 visit when filgotinib becomes commercially available, the Week 48 visit can replace or occur on the same day as the EoT visit (see Section 8.1.2). When the EoT visit is performed, the subjects will be considered as having completed the treatment part of the study and can start taking commercial filgotinib or local standard of care the next day. In addition, subjects will be requested to attend a follow-up visit 4 weeks after the EoT visit. The study will be terminated in that country when the last subject in that country has completed the safety follow-up visit.

Reduction in study visits

After unblinding at the study primary analysis time point, the frequency of study visits will be reduced to every 24 weeks (see Section 8.1.4). All subjects should be invited for an unblinding visit no later than 4 weeks after the study primary endpoint unblinding. If no regular visit is scheduled within this time frame, an unscheduled visit should be performed for IP dispensing to ensure the subject has sufficient IP to cover the period until the next 24-weekly visit.

Subjects who discontinue the study will be asked to attend an early discontinuation (ED) visit.

A schematic diagram of clinical study design, procedures, and stages is provided in [Figure 1](#).

[figure not shown]

Figure 1: Schematic Diagram

EoT: End of Treatment; EoS: End of Study; ES: endoscopic score; mMCS: modified Mayo Clinical Score; n: number of subjects in the treatment group; q.d.: once daily.

^a mMCS of ≤ 2 points, with endoscopic subscore of ≤ 1 , stool frequency subscore of ≤ 1 , and rectal bleeding subscore of 0.

^b EoS: when the last subject has completed the safety follow-up visit in that country (i.e. after completing minimum 48 weeks of treatment and the follow-up visit) OR (in countries where filgotinib is not commercially available) when the last subject completes 216 weeks in the study.

5.2. Clinical Study Design Rationale

The study is designed to evaluate the efficacy and safety of dose de-escalation of orally administered filgotinib in subjects with UC in clinical remission.

Subjects must have been in clinical remission for at least 2 consecutive quarterly visits in the SELECTION-LTE study prior to and including screening of the present study, to ensure that subjects are stable and that possible effects on efficacy can be attributed to dose change. Since UC is a progressive disease and worsening symptoms and flares can occur due to external factors as well as natural disease progression, a control group that remains on 200 mg filgotinib q.d. is included in the study design. The selected population will be recruited from subjects currently in the SELECTION-LTE study.

While the main objective of the study evaluates the possibility to maintain clinical remission while lowering the dose, subjects who do experience a flare will re-escalate to 200 mg filgotinib q.d. to evaluate if and how rapidly a response can be re-established.

Filgotinib is now approved for the treatment of UC in the EU, UK, and Japan, and shows a positive benefit-risk profile in patients with UC. To reduce the subject's burden in terms of both travel and site attendance, and assessments required, a reduction of on-site visit frequency will be introduced. After study unblinding at the primary analysis time point (see Section 6.4.2), the frequency of study visits will be reduced to every 24 weeks. In terms of safety data collection, prompt reporting and follow-up of any potential intermittent safety event is emphasized and continued on an ongoing basis.

The maximum study duration for a single subject in the present study is 216 weeks (approximately 4 years). This maximum duration is calculated based on the last subject enrolled and still included in the SELECTION-LTE study. Since subjects are recruited from SELECTION-LTE, they will be provided the opportunity to have the same length of treatment as in SELECTION-LTE.

[REDACTED]
[REDACTED]
[REDACTED] Patients with an active disease state will have elevated IL-6 plasma concentrations reported to decrease activity of carboxylesterase (CES)2 (Li et al., 2021; Shen et al., 2019), the enzyme involved in the metabolism of filgotinib into the active metabolite. [REDACTED]
[REDACTED]
[REDACTED]
[REDACTED]
[REDACTED]

5.3. Dosing Rationale

Doses have been selected based on efficacy and safety data in the preceding SELECTION and SELECTION-LTE studies.

5.4. Treatment Discontinuation, Subject Withdrawal

5.4.1. Treatment Discontinuation

The investigator, who may consult the medical monitor, can consider stopping the study treatment in case of concerns about the subject's safety, serious or severe AEs or worsening of

the disease condition, which in the investigator's opinion needs an alternative treatment approach not being covered in the clinical study. Every effort should be made to keep subjects in the study and on treatment, taking into account the subject's safety and well-being.

5.4.1.1. Permanent Treatment Discontinuation

Treatment with IP must be discontinued by the investigator (who may consult the medical monitor) for any of the following conditions:

- a. any opportunistic infection, defined at the discretion of the investigator;
- b. any serious infection that requires antimicrobial therapy or hospitalization, or any infection that meets SAE reporting criteria;
- c. febrile neutropenia (temperature $>38.3^{\circ}\text{C}$ or a sustained temperature of 38°C for more than 1 hour) with absolute neutrophil count of $<1000/\text{mm}^3$;
- d. symptomatic anemia (e.g. signs/symptoms including pallor, shortness of breath, new heart murmur, palpitations, lethargy, fatigue) with hemoglobin $<7.5\text{ g/dL}$, or if transfusion is indicated regardless of hemoglobin value;
- e. complicated herpes zoster infection (with multi-dermatomal, disseminated, ophthalmic, or central nervous system involvement);
- f. evidence of active hepatitis C virus (HCV) during the study, as evidenced by HCV RNA positivity;
- g. evidence of active hepatitis B virus (HBV) during the study, as evidenced by HBV DNA positivity;
- h. any thromboembolic event that meets SAE reporting criteria;
- i. unacceptable toxicity or toxicity that, in the judgment of the investigator, compromises the subject's ability to continue study-specific procedures or is considered to not to be in the subject's best interest;
- j. subject's request to discontinue for any reason;
- k. subject's noncompliance;
- l. pregnancy;
- m. subject's use of prohibited concurrent therapy;
- n. laboratory criteria: After becoming aware of any of the below described abnormal laboratory changes occurring at any one time, an unscheduled visit (i.e. sequential visit) should occur to retest within 3 to 7 days (except creatinine, which should be retested 7 to 14 days apart).
 - 2 sequential platelet counts $<75000\text{ platelets/mm}^3$ (SI $<75.0 \times 10^9\text{ cells/L}$);
 - 2 sequential aspartate aminotransferase (AST) or alanine aminotransferase (ALT) >3 times the upper limit of normal range (ULN) and at least 1 of the following confirmed values:
 - total bilirubin $>2\times\text{ULN}$;
 - or international normalized ratio (INR) >1.5 ;
 - or accompanied by symptoms consistent with hepatic injury.

For any subject with an initial AST or ALT elevation $>3\times\text{ULN}$, at the time of the second confirmatory blood draw, INR, prothrombin time (PT) and partial thromboplastin time (PTT) must also be assessed.

- 2 sequential AST or ALT elevations >5x ULN;
- 2 sequential values for estimated creatinine clearance (CrCl) <35 mL/min based on the Cockcroft-Gault formula¹.
- o. disease worsening (refer to Section 5.4.1.3);
- p. nonresponse to re-escalation therapy (refer to Section 5.1).
- q. subjects diagnosed with malignancy during the study except successfully treated non-melanoma skin cancer or cervical carcinoma in situ.

Any subject who discontinues study treatment, regardless of reason, will be invited to remain in the study and complete the visits as scheduled up to Week 48.

When the subject is discontinued from the study, the subject will be requested to return for the ED visit.

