5.4.1.2. Temporary Treatment Discontinuation

Where possible, IP should not be interrupted. In case IP interruption is needed as per the discretion of the investigator (e.g. for intercurrent illnesses, new infections, or elective or emergency surgeries), the medical monitor should be consulted prior to IP interruption when medically feasible.

IP interruption should be considered in the following circumstances:

- Subjects with newly positive (converted) or 2 indeterminate QuantiFERON® tuberculosis (TB) test (or centrally reported equivalent assay) result(s) should interrupt study drug dosing and be evaluated for active TB and latent TB by the investigator per local standard of care. An indeterminate result should be repeated once and the second result (if positive or negative) will be accepted. Positive or negative results must not be repeated.
 - Subjects diagnosed with latent TB (i.e. a subject who has newly identified positive diagnostic TB test result, in which active TB has been ruled out) may initiate an adequate course of prophylaxis as per local standard of care. Appropriate, ongoing, prophylactic treatment for latent TB must be initiated for a minimum of 4 weeks prior to the continuation of study medication. Subjects may resume study drug after investigator's consultation with medical monitor.
 - Subjects with positive or 2 indeterminate QuantiFERON® test result(s) who are determined as having neither latent nor active TB infection may continue participation in the study after consultation and approval from the medical monitor.
 - Any subject with active TB must be discontinued from the study.
 - Subjects who were previously treated for TB with a complete and adequate course of therapy as per local standard of care and as verified by the investigator do not need to have yearly QuantiFERON® tests. Subjects previously treated for TB should be

¹ Estimate of CrCl using serum creatinine level: CrCl (male) = ([140-age] × weight in kg)/(serum creatinine × 72); CrCl (female) = CrCl (male) × 0.85.

screened at least yearly for signs and symptoms consistent with reactivation of TB and any subject with active TB should be discontinued from the study.

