Given this study will be performed during a severe acute respiratory syndrome coronavirus 2 (SARS-CoV-2) pandemic, appropriate measures should be taken to minimize the risk of SARS-CoV-2 infection for subjects participating in the study as well as study site personnel. Local guidelines to prevent SARS-CoV-2 infection should be adhered to.

HBV Surveillance

- Subjects with positive HBV surface antigen (HBsAg) at screening were excluded from the parent UC studies (GS-US-418-3898 and GS-US-418-3899). Subjects who were positive for HBV surface antibody (HBsAb), but negative for both HBsAg and HBV core antibody (HBcAb) at screening were eligible to participate in the parent UC studies (GS-US-418-3898 and GS-US-418-3899) and are also eligible to participate in the present study.
- Subjects with positive HBcAb and HBV DNA below the lower limit of quantification (LLOQ) in a parent UC study will require ongoing HBV DNA monitoring every 12 weeks during the present study. After study primary analysis endpoint unblinding frequency will be reduced to every 24 weeks. These subjects may also require prophylactic treatment per investigator discretion in accordance with local guidelines/standard of care.
- Any subject who has HBV DNA \geq LLOQ will be discontinued from the present study (Section 5.4.1.1 and Section 6.2 item 10).

Malignancy has been reported in subjects on filgotinib. In the present study, subjects will be required to have up to date colorectal cancer screening and surveillance as per standard of care. Following SELECTION and SELECTION-LTE studies, subjects with recent malignancies will be excluded from the present study (Section 6.2, Item 9.1) and those diagnosed during the study will be discontinued, except successfully treated non-melanoma skin cancer or cervical carcinoma in situ.

Highly effective contraceptive measures are expected to mitigate the risk of fetal toxicity. Refer to Section 6.3.1 for further guidance on pregnancy precautions and contraceptive requirements.

For more details refer to the latest version of the IB and its relevant updates/addenda.

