EVENT	SCREENING PERIOD		TREATMENT PERIOD						FOLLOW-UP PERIOD	
	S1 ^a	S2	Day 1 ^b	W4	W12 and then every 12 weeks	W24 and then every 24 weeks	W48 ^c and then every 48 weeks	ED	EoT ^d	4 weeks after last IP dose (EoS)
	D-28 to D-1			± 3 days	± 7 days	± 7 days	± 7 days			± 3 days
Hematology		✓ ^{l, m}		✓	✓			✓	✓	✓
Chemistry		✓ ^{l, m}		✓	✓			✓	✓	✓
Lipid profile (fasted ⁿ)		✓ ^{l, m}				✓			✓	
Urine analysis		✓ ^{l, m}				✓			✓	
HBV DNA monitoring ^o		✓ ^l			✓				✓	
12-lead ECG		✓ ^l					✓		✓	
Serum immunoglobulin		✓ ^l				✓			✓	
CRP		✓ ^l		✓	✓			✓	✓	
Fecal calprotectin ^p	✓ ^q	✓ ^{l,r}		✓	✓			✓	✓	

^m Screening clinical laboratory results may only be available after randomization. In that case, these results will be reviewed after randomization and subjects with laboratory results meeting discontinuation criteria, will be discontinued from the study.

ⁿ Subjects should remain fasted for at least 8 hours, excluding water.

^o Only subjects with positive HBcAb and HBV DNA <LLOQ in a parent UC study will require ongoing HBV DNA monitoring every 12 weeks during the present study, and after study primary endpoint unblinding every 24 weeks.

^p Stool samples need to be taken prior to bowel preparation for endoscopy. Stool samples can be collected within 24 hours prior to the visit or during the visit.

^q FCP should be assessed during screening if the last assessment during SELECTION-LTE was >6 months prior to screening or the most recent value was >250 µg/g.

^r This FCP assessment should be obtained at the EoT visit in SELECTION-LTE (i.e. performed after the subject is fully eligible to roll over to the present study) and will be the baseline of the present study. In case FCP was not obtained at the EoT visit of SELECTION-LTE, an unscheduled stool sample should be collected within 24 hours prior to or during Day 1 (i.e. predose).

EVENT	SCREENING PERIOD		TREATMENT PERIOD						FOLLOW-UP PERIOD	
	S1 ^a	S2	Day 1 ^b	W4	W12 and then every 12 weeks	W24 and then every 24 weeks	W48 ^c and then every 48 weeks	ED	EoT ^d	4 weeks after last IP dose (EoS)
Study Day (D)/ Week (W)	D-28 to D-1			± 3 days	± 7 days	± 7 days	± 7 days			± 3 days
e-Diary instruction & review ^u			✓	✓	✓			✓	✓	✓
modified Mayo Clinical Score ^w	✓						✓	✓		

^a For subjects who consent to participate in the optional PK substudy, PK blood samples will be collected either at the Week 4 or Week 12 visit, or if more convenient, at any

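### Sections 5.4.1.1 and 5.5 give conflicting instructions for a subject who becomes HBV DNA positive on study: stop IP and stay to Week 48, or leave the study

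*Protocol*

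**What the plan says.** **Section 5.4.1.1 (treatment stop).** The list opens with "Treatment with IP must be discontinued by the investigator", so its items concern the drug and not study participation. Item g is "evidence of active hepatitis B virus (HBV) during the study, as evidenced by HBV DNA positivity". After the list comes the general rule: "Any subject who discontinues study treatment, regardless of reason, will be invited to remain in the study", with scheduled visits continuing to Week 48. The next sentence treats leaving the study as a separate act, followed by an ED visit.

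**Section 5.5, HBV Surveillance (study exit).** Any subject with HBV DNA at or above the LLOQ "will be discontinued from the present study (Section 5.4.1.1 and Section 6.2 item 10"). The two references are the treatment-stop list just described and an exclusion criterion about the discontinuation rules of SELECTION-LTE.

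**Section 8.9.1 (what is measured).** Footnote o says that HBcAb-positive subjects with HBV DNA below the LLOQ in a parent study "will require ongoing HBV DNA monitoring every 12 weeks during the present study". The row "HBV DNA monitoring ^o" is ticked at S2, at the 12-weekly visits and at End of Treatment (EoT). It is blank at ED and EoS. The copy of the schedule in SAP Section 2.4.1 has the same ticks.

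**Section 9.3.4.1 (how it is analysed).** The primary estimand counts any permanent treatment stop before Week 48 as nonresponse. The secondary estimand uses data collected after the stop. In both, a missing Week 48 value is primarily counted as nonresponse.

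**The concern.** A site with a positive HBV DNA result can follow either section and be compliant. One site keeps the subject off drug in the visit schedule; another sends the subject to an ED visit and closes participation. Two things depend on the choice.

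- **Safety data.** The course of HBV DNA after IP is stopped is either recorded every 12 weeks to Week 48 or not scheduled at all. Under Section 8.2, unscheduled safety results reach the CRF only if taken before the subject's last visit. Under Section 11.3.1, updates to an ongoing AE after the last follow-up visit stay in the source documents.
- **Secondary estimand.** It needs Week 48 outcomes from subjects who stopped treatment. A subject removed under 5.5 has none, so a coding rule takes the place of an observation that 5.4.1.1 would have offered to collect.

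**Working it through.** **1. The two instructions side by side**

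| | Section 5.4.1.1, item g | Section 5.5 |
|---|---|---|
| Trigger | HBV DNA positivity on study | HBV DNA at or above LLOQ |
| Action | Stop IP | Discontinue from the study |
| Afterwards | Invited to visits to Week 48, whatever the reason | Exit |
| Basis cited | – | 5.4.1.1 and 6.2 item 10 |

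Item g gives no threshold, but a result at or above the LLOQ is positive on any reading, so for such results both rules apply. Neither basis cited in 5.5 supports study exit: 5.4.1.1 prescribes only a treatment stop, and 6.2 item 10 is an entry criterion. Section 5.4.2 lets the investigator or sponsor withdraw a subject but does not say which events require it. No section states an exception or an order of precedence.

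**2. HBV DNA checks lost on exit**

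Inputs: 12-weekly checks (footnote o); follow-up offered to Week 48 (5.4.1.1); no tick at ED or EoS (8.9.1).

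Checks remaining = (48 − week of detection) / 12.

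| First positive result | Checks left if the subject stays | Checks left if removed |
|---|---|---|
| Week 12 | (48 − 12)/12 = 3 | 0 |
| Week 24 | (48 − 24)/12 = 2 | 0 |
| Week 36 | (48 − 36)/12 = 1 | 0 |
| Week 48 | 0 | 0 |

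The EoT tick does not fill the gap, because Section 8.1.2 ties that visit to commercial availability and completion of at least 48 weeks of treatment.

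**3. The plan's own precision figure, for scale**

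Protocol Section 9.1 states a worst-case 95% CI half width of 22.5 points with 40 per group, using Newcombe's continuity-corrected interval. At 20/40 versus 20/40 the continuity-corrected Wilson limits are 0.3406 and 0.6594, each 0.1594 from 0.5. The half width is √(0.1594² + 0.1594²) = 0.2254, or 22.5 points, so the figure reproduces. The conflict does not depend on it.

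**4. Bound for the secondary estimand**

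- One subject coded nonresponder who would have been in remission lowers that arm's rate by 1/40 = 2.5 points.
- The Mantel-Haenszel difference moves by the same amount if the endoscopic-score strata are balanced. With n_k subjects per arm in stratum k, the weight is n_k·n_k/(2n_k) = n_k/2 and the weights sum to 40/2 = 20. One subject moves the stratum difference by 1/n_k, so the overall change is (n_k/2)(1/n_k)/20 = 1/40.
- If the subject would not have been in remission, the change is 0. With an assumed remission probability of 0.25 to 0.75, the expected change is 0.25/40 = 0.6 to 0.75/40 = 1.9 points.
- Direction: removal from the 100 mg arm raises the 200 mg minus 100 mg difference; removal from the 200 mg arm lowers it.
- Primary estimand: the change is 0, because the treatment stop is already nonresponse.

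**The case against.** The case against giving this weight is substantial, and much of it stands.

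- **Safety cover.** Chemistry, which includes AST, ALT and bilirubin, is ticked at both ED and EoS. Section 11.3.1 requires ongoing AEs to be followed to resolution or stabilisation, and Section 11.3.2 requires SAE follow-up reports. A reader might infer that HBV-positive subjects are left without monitoring or care; the documents do not support that. What is lost is scheduled HBV DNA and its entry in the trial data.
- **Endpoints.** No primary or secondary endpoint visible in the documents uses HBV DNA. Early leavers have a sigmoidoscopy and mMCS at ED, so some outcome is collected. It is not a Week 48 value, however, and the protocol does not say that it may stand in for one.
- **Missing-data rule.** Section 9.3.4.1.2 makes nonresponse the main handling and leaves room for sensitivity analyses in the SAP. That softens the efficacy consequence but does not settle which instruction a site follows.
- **Other exits.** A reader might extend the point to active TB and to screening laboratory results read after randomization. For TB, Section 5.4.1.2 says "Any subject with active TB must be discontinued from the study"; TB is not a named item in 5.4.1.1, so this specific rule can be read as an exception to the general invitation. Schedule footnote m says that "subjects with laboratory results meeting discontinuation criteria, will be discontinued from the study". It does not say whose criteria are meant and can be read as late removal of subjects who fail eligibility. Neither shows the direct contradiction found for HBV.

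None of this reconciles 5.5 with the section that it cites.

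**Conclusion.** The conflict over on-study HBV DNA positivity is real in the current protocol text, and minor. Following 5.5 forgoes at most three scheduled HBV DNA checks per affected subject. It can move the secondary estimand by at most 2.5 points per affected subject in an arm of 40, and only if that subject would have been in remission at Week 48. The bound assumes the planned arm size and balanced strata. The documents give no rate of HBV positivity, so no expected bias can be stated; the number is likely to be small, since only HBcAb-positive subjects are monitored.

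A reader might infer that trial results are biased. The documents do not support that. The primary estimand is unaffected. The study stopped with 22 randomized subjects, before any reached Week 48 (SAP Sections 2.4.3 and 6.1), and the SAP only lists the available primary-endpoint data. The point concerns the protocol as designed and any reuse of its text.

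**What to change.** 1. In Section 5.5, replace the study-exit wording for HBV DNA at or above the LLOQ with an instruction that the subject permanently stops IP and is invited to remain in the study to Week 48 under Section 5.4.1.1.
2. In Section 8.9.1, and in the copy in SAP Section 2.4.1, tick HBV DNA at ED for HBcAb-positive subjects under monitoring, so that those who decline to stay have one further value.
3. Leave the active-TB exit rule and footnote m as they are. At most, name them in 5.4.1.1 as exceptions to the general invitation. Reversing either would be a separate trade-off that this point does not justify.

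Cost: one sentence, plus one assay at a visit that already draws blood, in few subjects. No visits are added, because 5.4.1.1 already offers them. If the sponsor does intend study exit for HBV, an explicit exception in 5.4.1.1 would also remove the contradiction, but the later HBV DNA and Week 48 data would still be lost.
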